***Please enter the Protocol Number you would like to use to reference the protocol:**

TTW Doppler

* This field allows you to enter an abbreviated version of the Protocol Title to quickly identify this protocol.

Is this a multi-site study (i.e. Each site has their own Principal Investigator)?

No

Does this protocol involve the use of animals?

Yes No

4.0 Project Information

4.1 * Has another IRB/HRPP reviewed this study or will another IRB/HRPP be reviewing this study? If Yes, answer the questions according to the IRB/HRPP Determination.

Yes No

IRB Name	Review Date	Determination
No records have been added		

4.2 * Is this a research study or a Compassionate Use/Emergency Use/HUD project?

Yes No

4.3 What type of research is this?

- Biomedical Research
- Clinical trial (FDA regulated)
- Behavioral Research
- Educational Research
- Psychosocial Research
- Oral History
- Other

4.4 Are you conducting this project in pursuit of a personal degree?

Yes No

4.6 * Is this human subjects research? (As defined by 32 CFR 219) Human subject means a living individual about whom an investigator (whether professional or student) conducting research:
(i) Obtains information or biospecimens through intervention or interaction with the individual, and uses, studies, or analyzes the information or biospecimens; or

(ii) Obtains, uses, studies, analyzes or generates identifiable private information or identifiable biospecimens.

Yes No

4.7 * Do you believe this human subjects research is exempt from IRB review?

Yes No

5.0

Personnel Details

5.1 List any Research Team members without EIRB access that are not previously entered in the protocol:

No records have been added

5.2 Will you have a Research Monitor for this study?

Yes
 No
 N/A

6.0

Data/Specimens

6.1 Does the study involve the use of existing data or specimens only (no interaction with human subjects)?

Yes No

7.0

Funding and Disclosures

7.1 Source of Funding:

Funding Source	Funding Type	Amount
: Other Defense Health Agency, USU TTW Program	: Research Development Testing and Evaluation (RDT&E) funds	1999990

Total amount of funding:

1999990

7.2 Do you or any other Investigator(s) have a disclosure of a personal interest or financial nature

significant with sponsor(s), product(s), instrument(s) and/or company(ies) involved in this study?

Yes No

If Yes, complete and attach Conflict of Interest forms for all key personnel

8.3 Are there international sites?

Attach international approval documents, if applicable, when prompted. Note: Ensure local research context has been considered

Yes No

8.4 Is this an OCONUS (Outside Continental United States) study?

Yes No

Select the area of responsibility:

Have you obtained permission from that area of responsibility? (This is a requirement prior to study approval)

Yes No

9.0 Study Details

9.1 Key Words:

Provide up to 5 key words that identify the broad topic(s) of your study

Tourniquet Development, Education, Doppler, Tourniquet Function

9.2 Background and Significance:

Include a literature review that describes in detail the rationale for conducting the study. Include descriptions of any preliminary studies and findings that led to the development of the protocol. The background section should clearly support the choice of study variables and explain the basis for the research questions and/or study hypotheses. This section establishes the relevance of the study and explains the applicability of its findings

Trauma is the leading cause of death in the United States for people ages 1 to 44; uncontrolled bleeding is a leading cause of those deaths.¹ Immediate hemorrhage control, even prior to the arrival of emergency medical services, can save lives during these emergencies. Since the launch of the Stop the Bleed (STB) campaign in 2015, the public has been empowered to stop life-threatening hemorrhage.² One of STB's five objectives is to equip every bleeding control kit with audio and visual instructions; this has not yet been achieved. Commonly used tourniquets, such as the Combat Application Tourniquet (CAT) or Special Operations Forces Tourniquet (SOF-T), do not provide audio instructions and are not designed to provide feedback to facilitate tourniquet application. A device that could facilitate application and provide real-time instructions and feedback could be immensely beneficial to both the public and the DoD, especially to minimally or untrained people such as DoD civilians, contractors, and dependents on military installations. To achieve the above mentioned STB's objective, the research team at the National Center for Disaster Medicine and Public Health is devoted to develop a layperson tourniquet with audio-visual instructions and performance feedback.

In January 2020, the research team conducted a pilot study to evaluate this novel layperson tourniquet in a community lay public sample recruited from at the NBC Health Expo in Washington, DC. Findings of this pilot study were promising. One highlight of the results was that the proportion of participants who applied the tourniquet correctly using the layperson tourniquet was significantly higher than that using the CAT (93.3% versus 6.3%). Moreover, for when asked about their favoritism toward the tourniquet, 93.3% favored the novel layperson tourniquet, whereas 68.8% favored the CAT.

In addition to research results, feedback provided by the participants in this pilot study allowed the research team and the manufacturing partner to make adjustments and improvements to the testing device. Now we have completed a pilot study evaluating overall user experience of the novel layperson tourniquet, our next step is to conduct a functionality study examining the function of this novel layperson tourniquet and to see if it performs on par with the CAT.

9.3 Objectives/Specific Aims/Research Questions:

Describe the purpose and objective(s) of the study, specific aims, and/or research questions /hypotheses

The objective of the study is to determine if the novel layperson tourniquet (SMART TQ)'s ability to occlude arterial blood flow is non-inferior to a Combat Application Tourniquet (CAT).

9.4 Study Design:

Describe study design in one to two sentences (e.g., prospective, use of existing records/data /specimens, observational, cross-sectional, interventional, randomized, placebo-controlled, cohort, etc.). Specify the phase – Phase I, II, III, or IV – for FDA-regulated investigational drug research

This study will be a single blinded, randomized clinical trial.

9.5 Target Population:

Describe the population to whom the study findings will be generalized

The study will benefit the general public.

9.6 Benefit to the DoD:

State how this study will impact or be of benefit to the Department of Defense

Research findings and information collected from this research study would help ongoing efforts of developing a layperson tourniquet.

10.0

Study Procedures, Data Management, and Privacy

10.1 Study Procedures:

Describe step-by-step how the study will be conducted from beginning to end

This study will be a single blinded, randomized clinical trial. The study will be conducted in a room at USU's Multidisciplinary Laboratories.

The study has two arms: SMART TQ is the experimental arm and CAT is the control arm..

The study will consist of three groups of individuals:

- **Medical professionals who apply the tourniquet (we will call this group, medical professionals in this protocol). Each medical profession will be assigned to a study arm and switch to the other study arm halfway to reduce practice effects and minimize biases. They will be identified via the research team's professional network.**
- **Volunteers who offer their legs for tourniquet application (we will call this group of individuals study participants).**
- **Blinded observers who will use a doppler to check and monitor pulse. Absence of the dorsalis pedis pulse will be used to indicate occlusion of blood flow. The pulse monitored by the blinded observers will be used as an outcome for this research study. The only person blinded in the study will be the person checking for a successful application by measuring the doppler pulse – that is the blinded observers. There will be a bedsheet, or similar screen, placed between the portion of the participant's leg that has the tourniquet applied and the participant's foot where the doppler pulse will be**

measured. In addition, the research team will provide blinded observers noise-canceling headphones to minimize the influence of audio instructions provided by the SMART TQ.

We will recruit two medical professionals and two blinded observers and consent volunteers (i.e., participants). The detailed information for the informed consent process is summarized in the later section.

Training Session

Two medical professionals will attend a training session prior to the study. The session will allow the study team to verify that medical professionals can apply both types of tourniquets successfully. We anticipate this training session lasting no more than one hour and will recruit one participant for the training session.

Study Session

Upon the completion of the informed consent, participants will be assigned study ID numbers and then randomly assigned to a study arm: SMART TQ or CAT. The study steps are below:

- A study participant enters the study room, completing a demographic information sheet and taking blood pressure, and then lies down with the face and torso facing up.
- To capture the baseline dorsalis pedis (DP) pulse: A blinded observer uses a doppler ultrasound to check DP pulse, the artery pulse on the surface of the foot. Doppler ultrasound is a small medical ultrasound machine that uses high-frequency sound waves to measure the amount of blood flow through the arteries and veins. The doppler ultrasound probe will be placed on the exposed foot, a pulse detected, and the location where the pulse is detected on that foot will be marked with an "X" using a surgical marker, and the doppler probed removed. This marked location will be where the doppler probe is placed later to determine whether there is a pulse.
- The research team member will measure the circumference of the leg at the area of tourniquet application. To keep the application location consistent across all the participants, we will mark where on the leg the tourniquet should be placed for each application.
- A medical professional records which leg will be used for tourniquet application (left leg or right leg)
- The medical professional applies the tourniquet. This is the first application of the tourniquet. *For tourniquet application, in order to signal medical professional stops tourniquet application (i.e., stops tightening the tourniquet), the doppler signals will be audible to medical professionals. Once the doppler signals stop, the medical professionals will stop applying/tightening the tourniquet.*
- Upon the completion of the tourniquet application, the blinded observer records the presence or absence of a dopplerable pulse. A blinded observer again uses a doppler ultrasound probe to check the dorsalis pedis (DP) pulse, the artery pulse on the surface of the foot, at the previously marked "X" location on the foot.
- The medical professional removes the tourniquet and the study participant takes a break.
- The medical professional places a blood pressure cuff first and then places a tourniquet over the blood pressure cuff. This is the second application of the tourniquet. The blood pressure cuff will be attached to a fluid (e.g., water)

pressure sensor to measure surface pressure under the tourniquet. The medical professional will tighten the tourniquet until the doppler pulse is eliminated. The medical professional will then read and record the pressure readings.

- **The medical professional removes the tourniquet.**

The procedures will then be repeated to a participant's other leg for the other arm. For example, if a participant is initially assigned to the CAT and uses the right leg for tourniquet application. The participant will then be in the SMART TQ arm for the left leg.

Termination Procedures

For the first tourniquet application on each leg, the observer will use doppler ultrasound to assess the participant's foot for a present or absent dorsalis pedis pulse. The observer will make the assessment at the location previously marked with a surgical marker. As soon as the pulse is determined to be present or absent, the observer will verbally tell the medical professional, "remove the tourniquet now."

For the second tourniquet application on each leg, the medical professional will tighten the tourniquet on top of the neonatal blood pressure cuff as described. The study team member will record the pressure. As soon as the pressure is noted, the study team member will tell the medical professional, "remove the tourniquet now."

Participant Post-study Assessment

Following the application of two tourniquets to both legs, the study team will ask the participant to rest while lying on the table for five minutes. After five minutes, the study team member will ask the participant the following questions:

- Do you have any persistent pain beyond mild aching at the application site?
- Do you have numbness, tingling, or other abnormal sensations?
- Does your leg feel weak?

If the answer is yes to any question, the team member will ask the participant to rest for five more minutes and re-ask the questions. If the answer to any question is still yes, the study team member will recommend that the participant seek medical care at an emergency department or with the participant's physician. If the study team member or participant is concerned that they are experiencing a medical emergency, they will call 9-1-1 and alert any of the medical professionals assisting with the study for assistance.

If the answer to the questions is no, the study team member will ask the participant to walk up and down the hall in the MDL. The study team member will observe the participant ambulating. If the person feels normal while walking, they can be discharged from the study.

The study team member will be advised to follow-up with their physician or emergency department for medical care if either leg develops worsening pain, swelling, redness, coldness, or bluish or pale color, or if they have shortness of breath or chest pain. The study team member will advise the participant that some mild local bruising or redness in the area of the tourniquet application may occur and that it does not require medical evaluation.

In addition, given the SMART TQ is an abbreviated investigational device, we will follow the abbreviation requirements specified by the FDA. Please see the "Devices" section for detailed information.

Describe all the data variables, information to be collected, the source of the data, and how the data will be operationally measured.

The outcome variables in the study are: 1. the participants' resting blood pressure, 2. the presence or absence of dorsalis pedis pulse after tourniquet application, and 3. the surface pressure reading when the tourniquet is tightened. At the beginning of the study, participants will be asked to complete a demographic information sheet. On this sheet, they will fill out their age, gender, race, and ethnicity. The demographic information sheet is attached to this protocol.

10.3 At any point in the study, will you request, use, or access health information in any form, including verbal, hard copy and electronic?

Yes No

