14.0 Risks and Benefits

14.1 Risks of Harm:

Identify all research-related risks of harm to which the subject will be exposed for each research procedure or intervention as a result of participation in this study. Consider the risks of breach of confidentiality, psychological, legal, social, and economic risks as well as physical risks. Do not describe risks from standard care procedures; only describe risks from procedures done for research purposes

The study will not collect any PHI and pose no significant risk to medical professionals who will apply the tourniquet and blinded observers. However, the study participants may experience minor pain or discomfort when a tourniquet is applied. Previous work has demonstrated temporary and minor pain with tourniquet use.³

14.2 Measures to Minimize Risks of Harm (Precautions, safeguards):

For each research procedure or intervention, describe all measures to minimize and/or eliminate risk of harms to subjects and study personnel

Given that medical professionals will be the ones who apply the tourniquet and on site, any discomfort or pain mentioned by study participants will be addressed immediately. Tourniquet application is anticipated to cause temporary pain when tightened (similar to a blood pressure cuff). If a participant expresses a desire to stop, the medical professional will stop immediately and remove the tourniquet, and recommend follow up if the pain does not quickly subside. The tourniquets will be applied for a very brief period of time - likely less than 60 seconds for each application. This brief application is very unlikely to cause vascular, nerve, or other tissue damage. Anyone with symptoms following tourniquet application will be instructed to follow-up with an emergency department or their physician as appropriate.

14.3

Confidentiality Protections (for research records, data and/or specimens):

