Because all study procedures will be conducted in person and medical professionals will apply tourniquets, any adverse events related to this study will be observed and addressed immediately.

Anticipated but not serious adverse events, such as minor discomfort or pain, will be reported on the Progress Report, which is generally performed on a 12-month cycle. More frequent Progress Reports may be required at the discretion of the IRB.

Serious adverse events are unlikely. Tourniquets left in place for prolonged periods of time (typically greater than 2 hours) have an increased risk of serious complications such as limb loss (amputation), compartment syndrome (muscle and nerve damage requiring surgery), and permanent nerve damage (weakness, numbness, pain in leg). We anticipate a very brief tourniquet application (no more than one minute) which will mitigate this risk.

Unanticipated adverse events will be identified by either medical professionals if a participant sees their physician or an emergency department, or research staff on-site if there is an immediate problem. Examples of less serious unanticipated adverse events include severe pain, extensive bruising, or temporary nerve injury (numbness, burning, pins-and-needles sensations).

All serious adverse events that are related to or may be related to study procedures will be reported by the PI within 24 hours by submitting an adverse event report to the IRB and a written follow-up report within 5 business days.

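### The temporary minor pain that the protocol expects and undertakes to report is never actively asked about in the visible procedures, so it is captured only passively

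*Combined protocol and SAP*

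**What the plan says.** **What is expected.** Section 14.1 says that "the study participants may experience minor pain or discomfort when a tourniquet is applied" and adds: "Previous work has demonstrated temporary and minor pain with tourniquet use". Section 14.2 describes the pain as temporary, arising on tightening, and expects each application to last under a minute.

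**What is to be reported.** Section 16.1: "Anticipated but not serious adverse events, such as minor discomfort or pain, will be reported on the Progress Report", which normally runs on a 12-month cycle.

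**What is asked.** The study steps and the termination procedures in 10.1 contain no symptom question during or just after any application. The questions come at the end, when both applications to each leg are done and the participant has had a five-minute rest lying down: "After five minutes, the study team member will ask the participant the following questions". There are three:

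- "Do you have any persistent pain beyond mild aching at the application site"
- "Do you have numbness, tingling, or other abnormal sensations"
- whether the leg feels weak.

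A yes leads to more rest, a repeat of the questions and, if still yes, a recommendation to seek care. A no to all leads to a walking check and discharge.

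**What is analysed.** The outcome variables listed in section 10 are resting blood pressure, pulse after application and surface pressure. Section 11.6 gives a chi-square test for the primary outcome and descriptive statistics for other study variables.

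**The concern.** The protocol names an expected harm and says it will be reported, but the question it scripts is worded and timed so that the expected harm does not qualify. The harm arises during tightening, is minor and passes. The question is put later, in the present tense, and sets a floor above mild aching.

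At stake is how complete the safety description of an investigational device will be. If minor pain enters the record only when someone speaks up or a staff member notices, the Progress Report reflects who happened to comment as much as what happened. Participants must have prior tourniquet experience so that they understand the discomfort (12.1). It is a reasonable inference, though not a documented fact, that such people may not think expected pain worth mentioning.

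**Working it through.** The plan gives no figure on this point to reproduce. The check sets the passages against one another and counts the occasions on which the event can occur.

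**Step 1. Occasions.** Inputs: up to 20 study-session participants (11.1, 11.2); two legs each, one per device, and two applications per leg (10.1).

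- Tightenings per participant: 2 × 2 = 4.
- Total: 20 × 4 = 80.
- Per device: 20 × 1 leg × 2 applications = 40.

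**Step 2. What the scripted pain question detects.** A truthful yes needs pain that is still present after the rest, persistent, and worse than mild aching.

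| Participant's experience | Class under 16.1 | Truthful answer |
|---|---|---|
| Minor pain on tightening, gone by the end | Anticipated, to be reported | No |
| Minor pain that has settled to mild aching | Anticipated, to be reported | No |
| Severe pain on tightening that settles before the question | Severe pain is a listed example of an unanticipated event | No |
| Pain beyond mild aching still present | Depends on severity | Yes, but the question does not ask which leg or device |

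The first two rows are the event that 14.1 and 14.2 describe. The other two scripted questions concern abnormal sensation and weakness at the same late time, so they do not fill the gap. Section 16.1 sorts pain by degree, and the form's own prompt there asks for a severity scale, but none is named.

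**Step 3. Other routes to the record.**

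- *Spontaneous mention* (14.2): pain that a participant raises is dealt with at once.
- *Staff observation* (16.1): adverse events are to be noticed and dealt with on the spot.
- *A request to stop* (14.2): the tourniquet comes off.

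All three can bring pain to light. Each is described by the response it triggers; none states a recording step, a scale or a link to a device.

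**Step 4. Size.** Let *p* be the share of tightenings that cause temporary minor pain and *m* the share of those that are mentioned or noticed and then written down.

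- Expected events: 80 × *p*.
- Found by the scripted question: 80 × *p* × 0 = 0, whatever *p* is, for events settled to mild aching or less.
- Reported: 80 × *p* × *m*, so the share missed is 1 − *m*.

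The documents give neither *p* nor *m*. The zero scripted yield needs no assumption about how common the pain is. The shortfall in the report depends on *m*, which could lie anywhere from 0 to 1.

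**The case against.** The strongest reply is that the three questions are a discharge check and were never meant as an adverse event form. That is right. Their only stated use is to decide on more rest, advice to seek care, or the walking check. The point is therefore not that the question is badly worded for its job, but that nothing else in the visible procedures asks actively.

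The second reply is that medical professionals are present at every application, and that spontaneous report plus observation is a recognised way to collect minor events. That also stands as far as it goes: passive collection is a legitimate choice. But the protocol does not state it as the method or say how such events are written down.

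The third reply concerns what is not in the file. The IRB correspondence lists an Observer Checklist whose contents are not included. If it carries a pain item, most of the point falls away and only a cross-reference is missing.

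A reader might also infer more than the documents support:

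- *That the pain can never be captured.* It can, through the passive routes.
- *That a no is logged as absence of pain.* Section 10.1 states no recording step for these answers.
- *That 16.1 promises a count or a breakdown by device.* It promises only an entry on the Progress Report.
- *That the trial fails to compare pain between devices.* No such comparison is planned. The objective in 9.3 is non-inferior arterial occlusion, and only the Doppler observers are blinded, so participants' pain ratings would be open-label.

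**Conclusion.** The gap is real but modest. On the visible text, the harm that 14.1 and 14.2 expect is never actively asked about at any of up to 80 tightenings, and the one scripted pain question cannot detect it once it has settled. What reaches the 16.1 report depends on mention or observation, with no stated recording step or device attribution, and is likely to be incomplete. Any percentage put on the shortfall would be an assumption, since the documents give no pain or mention rate.

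The conclusion rests on the Observer Checklist holding no pain item, which cannot be checked from the file. It concerns the safety description only. The primary occlusion outcome and its analysis are unaffected. This is an inexpensive improvement to the safety data, not a defect that threatens the trial's conclusion.

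**What to change.** Leave the three discharge questions and their follow-on steps as they are.

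1. In 10.1, add one recorded item straight after each tourniquet removal: *any pain or discomfort while it was on, or now?* (yes/no, or 0–10), with leg and device noted.
2. In 16.1, name these answers as the source for minor discomfort or pain on the Progress Report.
3. In 11.6, add a descriptive summary by device, labelled as unblinded self-report and not as a formal comparison.
4. If the Observer Checklist already holds such an item, cite it in 10.1 and 16.1 instead of adding a new one.

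The cost is four short questions per participant, at most 80 answers in all (20 × 4), and a line on the data sheet. No extra visit or staff is needed. The downside is that more minor events will be counted than under passive collection.

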12.4 Special categories, check all that apply

- Minors /Children
- Students
- Employees - Civilian
- Employees - Contractor
- Resident/trainee
- Cadets /Midshipmen
- Active Duty Military Personnel
- Wounded Warriors
- Economically Disadvantaged Persons
- Educationally Disadvantaged Persons
- Physically Challenged (Physical challenges include visual and/or auditory impairment)
- Persons with Impaired Decisional Capacity
- Prisoners
- Pregnant Women, Fetuses, and Neonates
- Non-English Speakers
- International Research involving Foreign Nationals - Headquarters Review is necessary

You must also consider the requirements of DoDI 3216.02, paragraph 7.e.

You must also consider the requirements of DoDI 3216.02, Enclosure 3, paragraph 7.e.

12.5 Inclusion Criteria:

Order Number	Criteria
1	Participants – Individuals with access to the USU campus and prior tourniquet experience

12.6 Exclusion Criteria:

Order Number	Criteria
1	Individuals younger than 18 years old or older than 65 years old
2	Individuals with the following conditions or history will be excluded from participation: hypertension, prior vascular surgery, peripheral vascular disease, diabetes, prior lower extremity vascular surgery, active lower extremity infection, any hypercoagulable condition (such as Factor V Leiden, or Protein C and S deficiency), pregnancy, or any condition in which the participant is concerned they may suffer harm from brief tourniquet application.
3	Individuals with any history of deep venous thrombosis or pulmonary embolism.

13.1 Please describe the recruitment process, including how subjects will be identified and selected for the study.

We will recruit 21 study participants, with 20 being study participants and one additional being the participant in the training session, from USU. We will obtain appropriate approvals to recruit participants. Recruitment will be conducted via passive methods, such as class announcements.

Individuals who are interested in this study can contact a member of the research team and the research team member will ask if the individual is able to complete the screening questions. Upon the completion of the screening questions, if eligible, participants' consent will be conducted in a private room or via private virtual method.

13.2 Compensation for Participation:

No compensation for participating in this research study.

13.3 Please describe the pre-screening process. If no pre-screening, enter Not Applicable in the text editor

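### Leg symptoms are asked about only after both devices have been used, without naming the leg, so a symptom present on arrival cannot be told from a new one or tied to a device

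*Combined protocol and SAP*

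**What the plan says.** Under Participant Post-study Assessment in 10.1, the participant rests for five minutes once both legs have had their two applications. Then: "After five minutes, the study team member will ask the participant the following questions". The questions are:

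1. "Do you have any persistent pain beyond mild aching at the application site"
2. "Do you have numbness, tingling, or other abnormal sensations"
3. "Does your leg feel weak"

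Any yes leads to five more minutes of rest and a second asking. After that, "If the answer to any question is still yes, the study team member will recommend that the participant seek medical care". If the answers are no, a team member watches the participant walk before discharge.

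At the start of the session the participant is described as "completing a demographic information sheet and taking blood pressure, and then lies down with the face and torso facing up". The foot pulse is then located and the leg circumference measured. The data-variables item that follows 10.1 lists demographic fields only for the entry sheet. The amendment approved in January 2021 adds age, sex and body measurements to it.

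Screening rests on the exclusions in 12.6, which include "hypertension, prior vascular surgery, peripheral vascular disease, diabetes, prior lower extremity vascular surgery, active lower extremity infection", clotting disorders, pregnancy, past thrombosis or embolism, and the volunteer's own worry about harm. The telephone questions in 13.3 repeat the conditions and end with an open invitation to mention anything else.

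Section 16.1 names temporary nerve injury, with numbness among its signs, as an example of a less serious unanticipated adverse event.

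**The concern.** Questions 2 and 3 ask about the present state, not about change. A participant with a long-standing patch of numbness or a weak leg from an old injury would truthfully answer yes both times, and so would a participant whose nerve had just been compressed. The planned data do not distinguish the two. The error can run either way: an old symptom may be put down to the tourniquet, or a real worsening may be dismissed as old.

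The missing leg adds a second loss. Each participant receives the investigational device on one leg and the control on the other, so the leg identifies the device. An answer that does not name the leg cannot be assigned to SMART TQ or CAT, even if it is known to be new. At stake is the attribution of any symptom reported for an investigational device in a sample of at most 20.

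**Working it through.** The plan states no figure on this point, so the main check is a reading of each step before and after application.

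**Before the first application: is any leg symptom recorded?**

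| Step | Where | Leg-symptom item? |
|---|---|---|
| Telephone screening | 13.3 | Conditions plus an open prompt; no question on current pain, numbness or weakness |
| Exclusions | 12.6 | Remove some causes (diabetes, peripheral vascular disease); nothing specific to back-related symptoms or old injuries |
| Entry sheet | 10.1, data-variables item, January 2021 amendment | None described |
| Blood pressure, foot pulse, circumference | 10.1 | None |

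**After application: how are the answers used?**

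| Use | Where | Finding |
|---|---|---|
| Rest, advice or discharge | 10.1 | Yes; this is their stated function |
| Outcome variable | Data-variables item | Not listed (blood pressure, pulse and surface pressure are) |
| Analysis | 11.6 | None named for symptoms |
| Adverse event rule | 16.1 | None turning a yes into an event, but numbness is an example of one and reporting is framed by relation to the study |

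The gap appears where the two tables meet. Judging whether a symptom is related to the procedure requires its state beforehand, and for comparing devices it requires the leg. Neither is planned to be collected.

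**Size, for illustration only.** Let p be the share of participants who arrive with a symptom that would produce a yes. The documents give no value, so p is an assumption. With n = 20 (11.2) and participants independent:

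- chance of at least one = 1 − (1 − p)^20
- expected number = 20 × p

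| Assumed p | Chance of at least one | Expected number |
|---|---|---|
| 1% | 1 − 0.99^20 = 18% | 0.2 |
| 2% | 1 − 0.98^20 = 33% | 0.4 |
| 5% | 1 − 0.95^20 = 64% | 1.0 |
| 10% | 1 − 0.90^20 = 88% | 2.0 |

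One participant is 1/20 = 5% of the sample. Each participant gives one leg to each device, so one affected leg is also 1/20 = 5% of the legs treated with that device.

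**The case against.** The strongest reply is that these questions are a discharge check, not a safety endpoint. They decide whether someone rests longer, is advised to seek care or goes on to the walking check, and for that purpose the present state is the sensible thing to ask about. This is correct, and it is why nothing here touches the referral or discharge steps.

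A reader might infer that a pre-existing symptom will be counted as tourniquet harm and will dominate the safety results. The documents do not support that. They contain no rule that counts or attributes a yes, no symptom outcome and no symptom analysis, and 16.1 speaks of events related to the study. A reader might also take the questions to be the only scripted safety step. They are not: 10.1 adds the observed walk and advice on warning signs, and 14.2 provides for removal on request.

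Three further points stand in part:

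- Question 1 is tied to the application site and to pain beyond mild aching, so it is less exposed than the other two.
- The open prompt in 13.3 and the self-judged exclusion give some chance of learning about an earlier leg problem, but neither asks about current symptoms or yields an answer for each leg.
- The screening questionnaire, observer checklist and demographic sheet are named but not reproduced, so an item on one of those forms cannot be ruled out. The protocol's own descriptions of the screening questions and the sheet show none.

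Staff could ask about onset when a yes occurs. That would be unplanned recall after the procedure, a weaker record than an answer given beforehand.

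**Conclusion.** The point holds as a minor, easily repaired gap in safety attribution. As the protocol is written, a symptom present on arrival cannot be told from a new or worsened one when an event is reported, and no symptom can be assigned to SMART TQ or CAT. Both statements rest on the protocol's descriptions of its steps and forms.

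The effect stops there. The primary outcome (pulse present or absent), its test and the sample size do not depend on these answers. The frequency of the problem is unknown. The 33% to 88% range follows from assumed prevalences of 2% to 10%, and also supposes that everyone with a symptom passes screening and answers yes both times.

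**What to change.** - **10.1, at entry:** ask the same three questions for each leg separately, alongside the demographic sheet and before the first application, and record the answers.
- **10.1, Participant Post-study Assessment:** record the answers for each leg separately. Without this, the baseline answers alone would not allow reporting by device.
- **Safety reporting (16.1, with a line in 11.6):** describe symptoms as new or worse than baseline, by leg and device.

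The referral and discharge steps remain as written. A participant with a stable old symptom would still follow the same pathway; the change affects what can be concluded from the answer, not what is done about it. The cost is under a minute per participant, a few lines on existing forms and a minor amendment. It has to be in place before the session, because a baseline cannot be reliably recovered once a tourniquet has been applied.
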